9.2.4 Additional Efficacy Analyses

Additional efficacy analysis includes the following endpoints at all visits in Period 1:

- Change from baseline in individual components of ACR response;
- ACR20/50/70 response rates;
- Change from baseline in DAS28 (CRP) and DAS28 (erythrocyte sedimentation rate [ESR]);
- Change from baseline in CDAI and SDAI;
- Change from baseline in morning stiffness (severity and duration);
- Proportion of subjects achieving change from baseline in HAQ-DI ≤ -0.22 for the subjects with baseline HAQ-DI ≥ 0.22 ;

- Proportion of subjects achieving change from baseline in HAQ-DI ≤ -0.3 for the subjects with baseline HAQ-DI ≥ 0.3 ;
- Proportion of subjects achieving LDA or CR based on DAS28 (CRP), DAS28 (ESR), Simplified Disease Activity Index (SDAI), and Clinical Disease Activity Index (CDAI) criteria;
- ACR/EULAR Boolean remission;
- Change from baseline in EQ-5D-5L;
- Change from baseline in SF-36;
- Change from baseline in Functional Assessment of Chronic Illness Therapy-Fatigue (FACIT-F);
- Change from baseline in Work Instability Scale for Rheumatoid Arthritis (RA-WIS).

For binary endpoints, point estimate and 95% CI using normal approximation will be provided for the response rate for each randomized treatment group. Point estimate, 95% CI and p-value will be provided for the treatment comparison between upadacitinib group and the placebo group using the Cochran-Mantel-Haenszel test adjusting for stratification factor country. The 95% CI will be based on normal approximation. NRI will be used as primary analysis and OC will be used as sensitivity analysis.

For continuous endpoints, the LS mean and 95% CI will be reported for each randomized treatment group. The LS mean treatment difference and associated 95% CI and p-values between upadacitinib group and the placebo group will be provided using MMRM model with fixed effects of treatment, visit and treatment-by-visit interaction, country and baseline value as covariates.

9.2.5 Handling of Multiplicity

In order to preserve Type I error, a step-down approach will be used to test the primary and ranked key secondary endpoints where statistical significance can be claimed for a lower ranked endpoint only if the previous endpoint in the sequence meets the requirements of significance. Specifically, the testing will utilize the endpoint sequence

of primary endpoint followed by ranked key secondary endpoints in the order as specified in Section 9.2.3, using α of 0.05.

9.2.6 Efficacy Subgroup Analysis

The primary efficacy endpoint will be examined in the subgroups listed in Table 6 below. Treatment difference between upadacitinib and the placebo group will be presented with point estimate and 95% confidence interval using normal approximation. No p-value will be provided for subgroup analysis. If any of the resulting subgroups (except for country subgroup) has fewer than 20% of the planned study size (i.e., < 64 subjects), the subgroup analyses for that variable will not be presented.

Table 6. Subgroups for Efficacy Analysis

Subgroup Factor	Categories
Age	< 40, [40, 65), \geq 65
Sex	Male or Female
Weight	< 60 kg or \geq 60 kg
BMI	< 25 or \geq 25
Country	China, South Korea and Brazil
Race	Asian, non-Asian
Duration of RA diagnosis	< 5 year or \geq 5 year
Baseline Rheumatoid Factor Status	Positive or Negative
Baseline Anti-CCP Antibody Status	Positive or Negative
Baseline both RF positive and Anti-CCP positive	Both positive vs at least one negative
Baseline both RF negative and Anti-CCP negative	Both negative vs at least one positive
Baseline DAS28 (hsCRP)	\leq 5.1 or $>$ 5.1
Concomitant csDMARD at baseline	MTX alone, MTX and other csDMARD, csDMARD other than MTX

9.2.7 Summary of Efficacy Analysis for Period 1

Table 7 below provides the overview of the efficacy analyses for Period 1 to be performed on different endpoints.

Table 7. Summary of Efficacy Variables and Corresponding Analyses for Efficacy Analysis in Period 1

Efficacy Variables	Analysis Method
Primary Variables	
• ACR20 response at Week 12	
 Point estimate and 95% CI of the response rate for upadacitinib group and placebo group. The 95% CI will be based on normal approximation. Point estimate, 95% CI and p-value for the treatment comparison between upadacitinib group and placebo group, where the p-value is constructed using the Cochran-Mantel-Haenszel test adjusting for stratification factor country. The 95% CI will be based on normal approximation. Subgroup analysis. Imputation: NRI for primary analysis and OC for sensitivity analysis Analysis Set: FAS and Per Protocol Analysis Set as supportive analysis (NRI only).
Key Secondary Variables	
Binary Endpoints:	
• Proportion of subjects achieving LDA based on DAS28 (CRP) ≤ 3.2 at Week 12	
 Point estimate and 95% CI of the response rate for each treatment group. The 95% CI will be based on normal approximation.
• Proportion of subjects achieving Clinical remission (CR) based on DAS28 (CRP) at Week 12	
 Point estimate, 95% CI and p-value for the treatment comparison between upadacitinib group and placebo group using the Cochran-Mantel-Haenszel test adjusting for stratification factor country. The 95% CI will be based on normal approximation.
• Proportion of subjects achieving LDA based on CDAI ≤ 10 at Week 12	
 Imputation: NRI for primary analysis and OC for sensitivity analysis
• ACR50/70 response at Week 12	
 Analysis Set: FAS
• ACR20 response at Week 1	

Table 7. Summary of Efficacy Variables and Corresponding Analyses for Efficacy Analysis in Period 1 (Continued)

Efficacy Variables	Analysis Method
Key Secondary Variables (continued)	
Continuous Endpoints:	
• Change from baseline in DAS28(CRP) at Week 12	
 LS mean, and 95% CI within each treatment group and LS mean, 95% CI and p-values between upadacitinib group and the placebo group using ANCOVA model with treatment, country and baseline value as covariates. Imputation: MI Analysis Set: FAS
• Change from baseline in SF-36 Physical Component Score (PCS) at Week 12	
 LS mean and 95% CI within each treatment group and LS mean, 95% CI and p-values between upadacitinib group and the placebo group using MMRM model with fixed effects of treatment, visit and treatment-by-visit interaction, country and baseline value as covariate. Analysis Set: FAS
Additional Variables (Summarized at all Visits up to Week 12)	
Binary Endpoints:	
• ACR20/50/70 response rate	
 Point estimate and 95% CI of the response rate for each treatment group. The 95% CI will be based on normal approximation.
• Proportion of subjects achieving change from baseline in HAQ-DI ≤ -0.22 for subjects with baseline HAQ-DI ≥ 0.22	
 Point estimate, 95% CI and p-value for the treatment comparison between upadacitinib group and the placebo group using the Cochran-Mantel-Haenszel test adjusting for stratification factor country. Only nominal p-value will be provided, and the 95% CI will be based on normal approximation.
• Proportion of subjects achieving change from baseline in HAQ-DI ≤ -0.3 for subjects with baseline HAQ-DI ≥ 0.3	
 Point estimate, 95% CI and p-value for the treatment comparison between upadacitinib group and the placebo group using the Cochran-Mantel-Haenszel test adjusting for stratification factor country. Only nominal p-value will be provided, and the 95% CI will be based on normal approximation.
• Proportion of subjects achieving LDA and CR based on DAS28(CRP), DAS28 (ESR), SDAI, and CDAI criteria	
 Imputation: NRI for primary analysis and OC for sensitivity analysis
• Boolean remission	
 Analysis Set: FAS

Table 7. Summary of Efficacy Variables and Corresponding Analyses for Efficacy Analysis in Period 1 (Continued)

Efficacy Variables	Analysis Method
Additional Variables (Summarized at all Visits up to Week 12) (continued)	
Continuous Endpoints:	

 Change from baseline in individual ACR components Change from baseline in DAS28 (CRP) and DAS28 (ESR) Change from baseline in CDAI and SDAI Change from baseline in morning stiffness Change from baseline in EQ-5D-5L Change from baseline in SF-36 Change from baseline in FACIT-F Change from baseline in RA-WIS 	
 LS mean and 95% CI within each treatment group and LS mean, 95% CI and p-values between upadacitinib group and the placebo group using MMRM model with fixed effects of treatment, visit and treatment-by-visit interaction, country and baseline value as covariate. Analysis Set: FAS

9.3 Long-Term Efficacy Analysis

Assessments to evaluate long-term efficacy will be analyzed for the following measures at Weeks 1, 2, 4, 8, 12, 16, 20, 24, 36, 48, and 64/PD:

- ACR20/50/70 response rates;
- Change from baseline in individual ACR components;
- Change from baseline in DAS28 (CRP);
- Change from baseline in DAS28 (ESR);
- Change from baseline in CDAI and SDAI;
- Change from baseline in morning stiffness;
- Proportion of subjects achieving change from baseline in HAQ-DI ≤ -0.22 for subjects with baseline HAQ-DI ≥ 0.22 ;
- Proportion of subjects achieving change from baseline in HAQ-DI ≤ -0.3 for subjects with baseline HAQ-DI ≥ 0.3 ;

- Proportion of subjects achieving LDA and proportion of subjects achieving CR based on DAS28 (CRP), DAS28 (ESR), SDAI, and CDAI criteria;
- Boolean remission;
- Proportion of subjects with no concomitant corticosteroid use (among subjects with corticosteroid use at baseline).

Assessments to evaluate long-term efficacy will be analyzed for the following measures at Weeks 4, 12, 24, 48:

- Change from baseline in EQ-5D-5L;
- Change from baseline in SF-36;
- Change from baseline in FACIT-F;
- Change from baseline in RA-WIS.

Descriptive statistics will be provided for each randomized treatment group sequence as defined in Section 9.1.1. These include the number of observations, mean, standard deviation, 95% CI, median, minimum, Q1, Q3 and maximum for continuous endpoints; and frequencies and percentages with 95% CI using normal approximation for binary endpoints. Plot for each randomized treatment group sequence over time will be provided up to Week 64.

No missing data imputation will be applied. All efficacy analyses will be based on As Observed (AO) analysis.

Table 8 below provides the overview of the long-term efficacy analyses to be performed on different endpoints.

Table 8. Summary of Efficacy Variables and Corresponding Analyses for Long-Term Efficacy Analysis

Efficacy Variables	Analysis Method
Binary Endpoints:	

 ACR20/50/70 response by visit Proportion of subjects achieving change from baseline in HAQ-DI ≤ -0.22 for subjects with baseline HAQ-DI ≥ 0.22 Proportion of subjects achieving change from baseline in HAQ-DI ≤ -0.3 for subjects with baseline HAQ-DI ≥ 0.3 LDA and CR based on DAS28(CRP), DAS28 (ESR), SDAI, and CDAI criteria by visit Proportion of subjects with no concomitant corticosteroid use (among subjects with corticosteroid use at baseline) Boolean remission 	
 Point estimate and 95% CI of the response rate for each randomized treatment group sequence Plot for each randomized treatment group sequence over time Imputation: AO Analysis Set: FAS
Continuous Endpoints:	

 Change from baseline in individual ACR components by visit Change from baseline in DAS28 (CRP) by visit Change from baseline in DAS28 (ESR) by visit Change from baseline CDAI and SDAI by visit Change from baseline in morning stiffness (severity and duration) by visit Change from baseline in EQ-5D-5L by visit Change from baseline in FACIT-F Change from baseline in RA-WIS Change from baseline in SF-36 by visit 	
 Point estimate, 95% CI of mean change from baseline together with SD, Min, Q1, Median, Q3 and Max for each randomized treatment group sequence Plot for each randomized treatment group sequence over time Imputation: AO Analysis Set: FAS

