**Table 5. Studies Activities (Period 2) (Continued)**

- b. At Week 24 (after Week 24 assessments have been performed), if a subject fails to meet LDA criterion (LDA defined as  $CDAI \leq 10$ ) investigator should adjust the subject's background RA therapies. Initiation of or change in corticosteroids, NSAIDs, acetaminophen, or adding or increasing doses of csDMARDs (concomitant use of up to 2 csDMARDs except the combination of MTX and leflunomide; see Inclusion Criterion 3) is allowed as per local label.
- c. Prior to other procedures. For morning stiffness, duration will be captured only if NRS rating is  $> 0$ .
- d. This is only applicable to subjects from China at Week 24.
- e. TB testing should be performed in all subjects with previous negative Quantiferon and/or PPD tests. Subjects with new evidence of latent TB should initiate prophylactic treatment immediately per local guidelines. Refer to Section 5.3.1.1 TB Testing/TB prophylaxis for additional details.
- f. An ECG may be performed at any visit if deemed necessary by the Investigator.
- g. Blood pressure, pulse rate, body temperature, and respiratory rate should be performed before blood draws are performed.
- h. A full physical exam is required at Week 24, Week 48 and Week 64/PD. A symptom-directed physical exam may be performed when necessary.
- i. Starting at Week 24 and thereafter, subjects who failed to show at least 20% improvement in TJC and SJC compared to baseline at 2 consecutive visits despite optimization of background RA therapies should be discontinued from the study.
- j. For women of childbearing potential, a urine pregnancy test will be performed at all visits and, starting at Week 24, monthly at home between scheduled study visits. The results of the monthly at home tests will be communicated to the site. If a urine pregnancy test is positive, the subject must stop dosing, come in to the clinic and have blood drawn for a serum pregnancy test that will be analyzed at the central laboratory. Pregnant subjects must discontinue from the study. Refer to Section 5.3.1.1 Study Procedures Pregnancy Test for additional details. If during the course of the study a woman becomes surgically sterile or post-menopausal and complete documentation is available, urine pregnancy test is no longer required.

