**5.4 Removal of Subjects from Therapy or Assessment****5.4.1 Discontinuation of Individual Subjects**

Subjects can request to be discontinued from participation in the study at any time for any reason, including but not limited to disease progression or lack of response to treatment. The Investigator may discontinue any subject's participation for any reason, including an AE, safety concerns, lack of efficacy, or failure to comply with the protocol. See Section 6.1.7 for toxicity management criteria.

Subjects will be withdrawn from the study immediately if any of the following occur:

- Clinically significant abnormal laboratory results or AEs, which rule out continuation of the study drug, as determined by the Investigator or the AbbVie Therapeutic Area Medical Director.
- Serious infections (e.g., sepsis) which cannot be adequately controlled within 2 weeks by anti-infective treatment or would put the subject at risk for continued participation in the trial as determined by the Investigator.
- The Investigator believes it is in the best interest of the subject.
- The subject requests withdrawal from the study.
- Inclusion or exclusion criteria violation was noted after the subject started study drug, when continuation of the study drug would place the subject at risk as determined by the AbbVie Therapeutic Area Medical Director.
- Introduction of prohibited medications or dosages when continuation of the study drug would place the subject at risk, as determined by the AbbVie Therapeutic Area Medical Director.
- Subject is non-compliant with TB prophylaxis (if applicable) or develops active TB at any time during the study.
- The subject becomes pregnant while on study drug.
- Malignancy, except for localized NMSC or carcinoma in situ of the cervix.
- Subject is significantly non-compliant with study procedures which would put the subject at risk for continued participation in the trial as determined by the Investigator.

- Subject develops a gastrointestinal perforation.
- Starting at Week 24, at least 20% improvement in BOTH TJC and SJC compared to baseline is required to remain in the study. Anyone who does not fulfill this criterion at 2 consecutive visits (starting at Week 24) must be discontinued from the study.

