9.1.2 Definition of Missing Data Imputation

Non-Responder Imputation (NRI) Approach

The NRI approach will categorize any subject who has missing value for categorical variables at a specific visit as non-responder for that visit. In addition, subjects who prematurely discontinue from study drug will be considered as non-responders for all subsequent visits after discontinuation.

Observed Cases (OC)

The OC analysis will not impute values for missing evaluations, and thus a subject who does not have an evaluation on a scheduled visit will be excluded from the OC analysis for that visit. In addition, the OC will not use values after premature discontinuation of study drug. This sensitivity analysis will only be applied to the analysis in Period 1.

As Observed (AO)

The AO analysis will not impute values for missing evaluations, and thus a subject who does not have an evaluation on a scheduled visit will be excluded from the AO analysis for that visit. Regardless of treatment switching or premature discontinuation of study drug, all observed data will be used in the analysis. The AO analysis will be applied to long-term efficacy analysis.

Mixed Effect Model Repeat Measurement (MMRM)

The repeated measure analysis will be conducted using mixed model including observed measurements at all visits. The mixed model includes the categorical fixed effects of treatment, visit and treatment-by-visit interaction, main stratification factors at randomization, and the continuous fixed covariates of baseline measurement. An unstructured variance covariance matrix will be used. The parameter estimations are based on the assumption of data being missing at random and using the method of restrictive maximum likelihood (REML). The missing at random assumption is considered reasonable given the high placebo response rate typically seen in RA trials. Additionally, in RA trials, the proportion of discontinuation is relatively small (10 – 15% only) and the rate of discontinuation due to lack of efficacy is generally low (< 5%).

Multiple Imputation (MI)

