- $ACR_{xx} = 0$ if TJC indicator = 0 OR SJC indicator = 0 OR at least 3 out of 5 components improvement indicators = 0.
- $ACR_{xx} = 1$ if TJC indicator = 1 AND SJC indicator = 1 AND at least 3 out of 5 components improvement indicators = 1.
- For all other cases, ACR_{xx} = missing since ACR_{xx} cannot be determined.

The following table illustrates examples for ACR calculations.

Example	TJC 68	SJC 66	Component 1	Component 2	Component 3	Component 4	Component 5	ACR20- Response?
A	1	1	1	1	1	.	.	Yes
B	1	0	1	1	1	1	1	No
C	.	0	No
D	1	.	1	1	1	1	1	.
E	1	1	0	0	0	1	1	No
F	.	.	0	0	0	.	.	No
G	1	1	1	1	0	0	.	.

Legend: 1 = \geq 20% improved compared to baseline; 0 = < 20% improved compared to baseline; " ." missing.

Windowing Rule for ACR Response Calculation:

- ACR component values will first be determined at each date within a visit window.
- ACR component values at each date will be combined to determine the observed ACR composite score at each date in each window.
- After this calculation, if multiple non-missing ACR composite scores are available within a given visit window, the non-missing ACR composite score

closest to the target day will be used. If two composite scores have the same distance from the target day, the later one will be used. The corresponding date will be used as the observed ACR response date in the derived efficacy dataset.

- If a non-missing ACR composite score is not available for any day within a given visit window, the windowed component values for that visit will be used to calculate the ACR composite score for that visit window (component value windowing follow the same rules as in steps described above). The date of observed ACR composite score will be determined by the first available ACR component date, in the order of TJC, SJC, Pain, PGA, PhGA, HAQ-DI, CRP/ESR, in the derived efficacy dataset.

When observed ACR xx response for a given visit is missing, imputation methods will be used to calculate "imputed" ACRxx response.

Non-Responder Imputation (NRI) for ACR response:

- Step 1: all missing components will be imputed using LOCF, and then the ACR composite score can be calculated.
- Step 2: if the ACR composite score cannot be determined by Step 1, the ACR composite score will be imputed as 0. In addition, subjects who prematurely discontinue from the study drug will be considered as non-responders (ACR = 0) for all subsequent visits after the discontinuation date.

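### Long-term ACR rates are shown As Observed only, although subjects who fail the joint-count rule at Weeks 24 and 36 leave the Week 48 denominator; an NRI display and removal counts should stand beside them

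*SAP*

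**What the plan says.** SAP 9.3 covers long-term efficacy from Week 1 to Week 64 and states: "No missing data imputation will be applied. All efficacy analyses will be based on As Observed (AO) analysis". Table 8 repeats this for the binary endpoints: "Imputation: AO Analysis Set: FAS". Under the AO definition in SAP 9.1.2, "a subject who does not have an evaluation on a scheduled visit will be excluded from the AO analysis for that visit".

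Protocol 5.4.1 requires at least 20% improvement from baseline in both tender and swollen joint counts from Week 24, and adds: "Anyone who does not fulfill this criterion at 2 consecutive visits (starting at Week 24) must be discontinued from the study". SAP 4.2 carries the same rule. Note i to Table 5 of the protocol words it differently, for subjects who fail "at 2 consecutive visits despite optimization of background RA therapies should be discontinued from the study".

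SAP 9.4.1 sets the observed ACR response to 0 "if TJC indicator = 0 OR SJC indicator = 0 OR at least 3 out of 5 components improvement indicators = 0". The same section defines NRI for ACR: first "all missing components will be imputed using LOCF", and any response still undetermined is set to 0. A further sentence there says that "subjects who prematurely discontinue from the study drug will be considered as non-responders (ACR = 0) for all subsequent visits after the discontinuation date". NRI is assigned to the Period 1 binary endpoints (SAP 9.2 and Table 7) but to no Period 2 display.

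**The concern.** Ordinary dropout may or may not be related to response. Here the protocol selects subjects for removal on two required components of the ACR endpoint, and the AO analysis then drops them from later denominators. What remains is a group from which some known non-responders have been taken out.

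Long-term efficacy is a stated Period 2 objective, and the SAP plans rates, 95% confidence intervals and plots to Week 64. A reader who sees the ACR curve rise after Week 36 could take it as continuing improvement when part of the rise comes from the shrinking denominator. The planned outputs do not let that reader separate the two. SAP 7.0 tabulates discontinuation for lack of efficacy, but not by visit, and nothing says that joint-count removals are coded to that reason.

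**Working it through.** The plan gives no long-term response rate or Period 2 dropout figure, so there is no stated number to reproduce. The check covers timing, ACR status and arithmetic.

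**1. Timing.** Period 2 visits are at Weeks 16, 20, 24, 36, 48 and 64/PD (Protocol 5.1). The first pair of consecutive scheduled visits under the rule is Weeks 24 and 36, so the first removals follow Week 36 and the first depleted visit is Week 48. A subject who fails at Weeks 36 and 48 is still observed at Week 48.

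**2. ACR status.** Take the rule's counts to be the TJC68 and SJC66 collected at each visit. Failing the rule then means that at least one joint indicator is 0, so ACR20, ACR50 and ACR70 are all 0 at both failing visits.

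**3. Could a discontinuation visit fill the Week 48 slot?** AO keeps data collected after study drug stops, but these subjects leave the study. The SAP has no window table for Period 2 and says only that windows follow the Period 1 pattern. Target days are 7 × week + 1: Day 253 for Week 36, Day 337 for Week 48 and Day 449 for Week 64. The Table 1 upper bounds of 22, 43 and 71 are the midpoints between neighbouring targets. On that pattern the Week 36/48 boundary is (253 + 337)/2 = Day 295. A Week 36 visit at the end of its 7-day window, followed by a discontinuation visit within the preferred 2 weeks, falls by 253 + 7 + 14 = Day 274. It maps to Week 36, not Week 48.

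For Week 64 the same arithmetic gives a boundary of (337 + 449)/2 = Day 393 and a latest discontinuation visit of 337 + 7 + 14 = Day 358. Windowed by study day, that visit would not count as Week 64. The label 64/PD could instead mean that such visits are pooled with Week 64.

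**4. Size.** Let O be the number observed at the visit, R the number removed by the rule and k the responders.

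- AO rate = k/O
- Rate with removed subjects counted as non-responders = k/(O + R)
- Difference = k/O − k/(O + R) = (k/O) × R/(O + R) = AO × s, with s = R/(O + R)

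| s | AO 60% (assumed) | AO 80% (assumed) |
|---|---|---|
| 1% | 0.6 points | 0.8 points |
| 2% | 1.2 | 1.6 |
| 3% | 1.8 | 2.4 |
| 5% | 3.0 | 4.0 |

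**5. A rise with no one improving (all counts assumed).** At Week 36, 290 subjects are observed and 220 respond: 220/290 = 75.9%. Fifteen of the 70 non-responders have now failed the rule twice and leave. At Week 48 the same 220 respond among 275: 220/275 = 80.0%. The rise is 4.1 points, which equals 0.80 × 15/290.

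**The case against.** The plan is open about what it does. AO is defined, labelled in Table 8 and not tested, and Protocol 8.1.4.2 asks only for descriptive summaries. Nothing here contradicts the protocol. All of that stands.

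Part of the remedy can already be approximated. SAP 9.3 prints frequencies as well as percentages, and SAP 7.0 gives the size of the FAS and the number entering Period 2, so a reader can divide responders by either total. This is close to NRI if few visits are missed intermittently. It still does not show how many subjects the joint-count rule removed by each visit.

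The only anchor for s is the SAP's remark that lack-of-efficacy discontinuation in RA trials is generally below 5%. That is a general statement supporting the missing-at-random assumption, not a forecast for Period 2. It covers all lack-of-efficacy exits, whereas by Week 48 the rule has removed only those failing at both Weeks 24 and 36. The effect may well be small beside sampling error: at an AO rate of 80% with 275/2 = 137.5 observed per sequence, the 95% half-width is 1.96 × √(0.16/137.5) = 6.7 points. However, the interval does not account for a shift caused by selection.

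A reader might infer more than the documents support:

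- *That AO overstates the true Week 48 response rate.* Status after removal is not observed, and background therapy may be changed from Week 24 (Protocol 5.2.3.1). Non-response at Week 48 is an NRI convention. AO is at least as high as NRI for any kind of exit, so that inequality alone does not prove bias.
- *That the whole gap between AO and NRI is due to the rule.* Add 32 other exits to the example (borrowing the 10% planning dropout rate) and use all 322 subjects. NRI is then 220/322 = 68.3%, and the gap is 11.7 points. Only 4.1 come from the rule; about 7.5 come from the assumed other exits.
- *That low disease activity, remission and HAQ-DI responder rates are affected in the same way.* This is likely, but it does not follow from their definitions.

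**Conclusion.** The point holds for ACR20/50/70 at Week 48. Following the plan drops observed ACR non-responders from that denominator and provides no display that counts them. The excess attributable to the rule is AO × s, about 0.6 to 4 points for s of 1–5% and AO of 60–80%. Both ranges are assumptions.

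The conclusion rests on the rule using TJC68/SJC66, on removal following scheduled visits, and on removed subjects having no later evaluation. Week 64 is affected if discontinuation visits are windowed by study day, but not clearly so if they are pooled with Week 64. The Week 12 endpoints and type I error are untouched. This is a gap in how the long-term results can be read, and a worthwhile, inexpensive improvement rather than an error in the confirmatory analysis.

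**What to change.** In SAP 9.3 and Table 8:

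- Keep AO and add an NRI display of long-term ACR20/50/70, using the algorithm in 9.4.1 and counting subjects as non-responders after study drug discontinuation.
- For Period 2 visits, use the subjects who entered Period 2 as denominator. If the FAS is used instead, state that Period 1 dropouts then count as long-term failures, including placebo-sequence subjects who never received upadacitinib.
- At any data cut, leave out ongoing subjects who have not yet reached the visit.
- At each visit, print the observed N and the cumulative number removed under the joint-count rule.
- State whether discontinuation visits are assigned by study day or pooled with Week 64.

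Protocol 5.4.1 and Table 5 note i must be reconciled, because the number removed depends on which wording sites apply.

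The cost is SAP wording, one extra table set using methods already defined, and a by-visit count of removals. The drawback is that NRI rates will be lower and conservative, since exits for adverse events and administrative reasons also count as failures. For that reason AO should stay beside them.
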